To understand if MDA might be effective at reducing GAS outside of the context of scabies control, and to better understand how, when and where MDA should be used in future in regions such as The Gambia, it is essential to understand the natural history of GAS carriage, persistence, transmission dynamics and clinical infection. We have shown a high level of GAS skin infections in The Gambia in a cross-sectional study, but in order to understand the temporal relationship between carriage and disease, how GAS is spread from person to person, via skin or pharynx, acquired inside or outside households, and other risk factors for carriage and disease, a longitudinal study is essential. Very few longitudinal studies of GAS exist (12, 23), and high quality data from high-prevalence countries in sub-Saharan Africa combining classical epidemiology with detailed social-mixing behaviour and next generation WGS techniques to model disease transmission will be highly informative in growing our understanding of GAS epidemiology.

2 Study objectives

Primary:

1. To determine the prevalence, incidence, duration and transmission dynamics of asymptomatic GAS carriage and clinical GAS infections within households.
2. To establish risk factors for pharyngeal and skin clinical GAS infection, including detailed characterisation of the relationship with individual and household asymptomatic carriage, *emm* type and seasonality.
3. To develop a mathematical model of household GAS transmission using clinical, behavioural and phylogenetic relatedness data to calibrate it, to allow for estimation of the relative contributions of between and within household transmission.

Secondary:

1. To determine risk factors for asymptomatic GAS carriage.
2. To describe the relative importance of asymptomatic GAS skin and throat carriage in this setting.
3. To describe any seasonal variation in GAS carriage and clinical GAS infection throughout the year.
4. To describe GAS *emm* type diversity in this setting.
5. To investigate the extent of GAS tissue tropism of *emm* types identified.
6. To determine the prevalence and incidence of groups C and G streptococcal carriage and clinical infection in this setting.
7. To describe variations in bacterial density by site, season and clinical characteristics using quantitative PCR.
8. To describe anti-GAS seroprevalence and investigate serological responses to asymptomatic GAS carriage and clinical GAS infection.

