3.2.3 Estimating GAS infection incidence

To assess incidence of clinical GAS disease in the cohort throughout the study, all participants reporting symptoms suggestive of possible clinical GAS infection such as pharyngitis or pyoderma (but also including invasive infections), will be visited for an unscheduled visit where a clinical and

health-seeking history will be recorded, a swab, saliva and DBS taken, and treatment (or further management) will be delivered according to WHO guidelines or best local practice. Furthermore, at each scheduled visit, any individual identified with symptoms of clinical GAS infection will undergo the same process of history-taking, swabbing, treatment and follow up.

4 Selection and withdrawal of participants

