5.3.4 Unscheduled visits for possible GAS infection

At any point during a participant's enrolment in the study, they may develop symptoms consistent with a superficial GAS infection (acute pharyngitis or pyoderma), a severe GAS infection, or an acute reaction to a GAS infection such as acute rheumatic fever (ARF). This may occur, or be picked up, at a scheduled monthly or weekly visit, but could occur at any other time. If this occurs between scheduled visits, they will be asked to contact the on-call study nurse, who will take details of the complaint over the phone, and depending on the severity of the symptoms will arrange for the participant to be seen either urgently at the MRC Unit Clinical Services Department, or less urgently at their compound the next day (or as soon as reasonably possible). The study nurse will be able to consult with the PI or another delegated clinician for medical advice.

In the case of a non-urgent visit, the study nurse will collect data on the history of the complaint, any medication taken and other relevant information. They will perform a physical examination, including vital signs. If the symptoms are consistent with possible GAS infection (pharyngitis or pyoderma), then a study swab will be taken (throat or wound) for culture alongside a saliva sample and a dried blood spot test. Treatment will be provided for pyoderma according to WHO or local guidelines. For suspected pharyngitis, treatment will be provided empirically based on WHO or local guidelines, and then reviewed following the culture result.

In the case of urgent visits at the Clinical Services Department, a study team member will attend the ward to collect this data as soon as possible, and take the study swab if applicable (ideally prior to any antibiotic therapy). Any further investigations performed and treatment given by the clinical services team will be recorded. In the case of suspected invasive GAS infection, the patient would be admitted for treatment. A blood culture should be performed as part of clinical assessment and if GAS is identified, the isolate will be obtained from the clinical microbiology laboratory for further analysis including whole genome sequencing. In the case of invasive GAS or suspected ACF the study team would obtain a separate serum sample.

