5.3.6 Weekly visits for asymptomatic GAS (or GCS/GGS) carriers

All participants not already in the intensified incident GAS cohort, who's OPS or NSS grow GAS (or GCS/GGS) on culture at a monthly visit following a previous negative swab, will be classified as "new carriers" who will then be swabbed weekly until such time as 2 negative swabs in a row have been obtained from the same site that was positive i.e. a participant who's OPS was positive at MV1 will have weekly OPS until negative twice in a row, whereas a participant with a positive NSS will have weekly NSS.

At these weekly visits, only the household member who is a "new carrier" will be seen and swabbed, not the other household members. The study team will ask a brief medical history, perform a physical examination, and take the swab from the previous positive site. If the participant has developed any clinician symptoms potentially in connection with their positive swab, then they will be treated as a GAS infection case as described in section 5.3.4.

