5.5.4 Clinical examination and vital signs

At the enrolment visit, all participants will undergo a physical examination including vital signs to provide a baseline. Vital signs collected will include axillary temperature, pulse rate and respiratory rate. Adults (over 18 years) will also have blood pressure recorded.

Participants will then undergo a physical examination which will include an examination of the pharynx and associated lymph nodes, and a full body examination of the participant's skin, to identify any pyoderma lesions, and other relevant skin conditions. Care will be taken to perform the full body examination with appropriate privacy and verbal consent obtained at the time. Portable screens will be used to maintain privacy when necessary. Participants' genitals will only be examined if they specifically report (or the parent reports, in the case of children) the presence of a lesion and verbally consent for the study nurse examine them.

At later scheduled visits, monthly visits for the main cohort, and weekly visits for the more intensive cohorts, participants will undergo the physical examination including throat and skin, but will not have vitals and anthropometry recorded unless they are reporting symptoms suggestive of a GAS infection. If they are symptomatic, a clinical history will be taken and fuller clinical examination of the presenting complaint will be done, in addition to recording vital signs.

At unscheduled visits participants will also have their vitals recorded in the same way, and a clinical history and focused clinical examination will be done.

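### Weekly examination triggered by a new positive swab biases the objective 2 carriage–infection association upward during that follow-up, by an amount the protocol does not let one derive

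*Protocol*

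**What the plan says.** Primary objective 2 (protocol section 2) is to establish risk factors for clinical GAS infection, "including detailed characterisation of the relationship with individual and household asymptomatic carriage". Incidence of clinical infection is also a primary endpoint (section 2.1).

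The examination schedule is in section 5.5.4: "monthly visits for the main cohort, and weekly visits for the more intensive cohorts, participants will undergo the physical examination including throat and skin". Entry to the weekly carrier schedule depends on the exposure itself, a swab that grows GAS (or GCS/GGS) "on culture at a monthly visit following a previous negative swab" (section 5.3.6). At those visits staff take a history, "perform a physical examination, and take the swab from the previous positive site". Only the new carrier "will be seen and swabbed, not the other household members". On symptoms, the section reads "If the participant has developed any clinician symptoms potentially in connection with their positive swab", and sends the person to the section 5.3.4 procedure.

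Infections found this way enter the common case route. Section 3.2.3, on estimating infection incidence, states that "at each scheduled visit, any individual identified with symptoms of clinical GAS infection will undergo the same process of history-taking, swabbing, treatment" and follow-up. Section 5.3.4 says of a possible infection: "This may occur, or be picked up, at a scheduled monthly or weekly visit, but could occur at any other time". Section 6.1.1.1 defines acute GAS pharyngitis as a positive throat culture with any one listed symptom (fever and cough are on the list) or any one listed sign.

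Three features work the other way. All participants may phone the on-call nurse (sections 5.3.4 and 6.1.2). Every member of 16 households is examined up to weekly for six weeks (section 5.3.5). Both pharyngitis and pyoderma need a positive GAS culture to count as GAS disease (section 6.1.1).

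**The concern.** A new carrier is examined about four times as often as a comparable non-carrier, for as long as the swabs stay positive and until two negatives follow. A short or mild infection that would clear between two monthly visits is likely to be found in the carrier and missed in the non-carrier unless the latter phones. The staff at the weekly visit would know why they are there. This is inferred, but the visit exists only because of the positive swab, and symptoms are considered in relation to it.

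The pharyngitis definition adds to this. A throat carrier is likely to be culture-positive still, so each extra visit is a further chance for an incidental cough or fever to turn carriage into a counted infection.

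At stake is the reading of objective 2. Carriage could appear to raise the risk of clinical infection when part or all of the excess comes from looking more often. Infection incidence by carriage state has the same weakness.

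**Working it through.** **Plan's own figure.** The protocol gives no figure for the carriage–infection association. Its only worked calculation (section 8) is for carriage prevalence: 1.96² × 0.15 × 0.85 / 0.05² = 195.9, rounded up to 196; × 2 = 392; × 1.10 = 431. It reproduces, but has no bearing on this point.

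**Inputs**
- From the protocol: examination every 7 days for new carriers and every month (365.25/12 = 30.4 days) for others.
- Assumed, because the protocol gives neither: episode duration d of 7 to 14 days, and probability s of self-report of 20% to 80%.
- Simplifications: visits on time, onset uniform between visits, an episode present at a visit always detected, self-report the same for carriers and non-carriers.

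**All detected infections, true ratio 1**

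Apparent ratio = [s + (1 − s) × min(1, d/7)] / [s + (1 − s) × d/30.4]

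| d (days) | s = 0.2 | s = 0.5 | s = 0.8 |
|---|---|---|---|
| 7 | 1/0.384 = 2.60 | 1/0.615 = 1.63 | 1/0.846 = 1.18 |
| 14 | 1/0.568 = 1.76 | 1/0.730 = 1.37 | 1/0.892 = 1.12 |

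With s = 1, or with equal schedules, the ratio is 1.00.

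**Dilution.** These ratios apply to time on weekly follow-up. If half of carrier time is weekly (d = 7, s = 0.5), the ratio is (0.5 × 1 + 0.5 × 0.615)/0.615 = 1.31 rather than 1.63.

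**Incidental symptoms.** Assume a 5% chance per examination of a listed symptom unrelated to GAS, in someone culture-positive throughout. One examination yields a case with probability 5%; four yield 1 − 0.95⁴ = 18.5%, or 3.7-fold. The table does not include this.

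**Monthly and participant-initiated detections only.** Suppose an infection found and treated at a weekly visit can no longer be captured later. With d = 14, a carrier infection that is not self-reported counts only if the first visit after onset is the monthly one: 7/30.4 = 0.23, against 14/30.4 = 0.46 for a non-carrier.
- s = 0.2: (0.2 + 0.8 × 0.23)/(0.2 + 0.8 × 0.46) = 0.68
- s = 0.5: (0.5 + 0.5 × 0.23)/(0.5 + 0.5 × 0.46) = 0.84

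At d = 7 both probabilities are 0.23 and the ratio is 1.00. All these values fall further if weekly visits also pre-empt some self-reports.

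**Equal-surveillance block.** 16 households × 10 people × 6/52 years = 18.5 person-years, which is 16/45 × 6/52 = 4% of household follow-up. Section 8 gives 592 skin infections per 1000 child-years, about half due to GAS, so roughly 0.3 per year. Applied to all ages, that is 18.5 × 0.3 = 5 to 6 skin events, of which about one would be in carriers at 15% carriage. Pharyngitis would add an unknown number.

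**The case against.** **Which infections enter the objective 2 model is normal SAP content, and the SAP is not shown.** This is fair as far as it goes: sections 3.2.3 and 5.3.4 describe a case route, not a regression. A SAP could limit the damage. It cannot undo the unequal schedule, which the protocol fixes, and separating events by how they were found requires that this be recorded.

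**Culture confirmation is objective.** It is. Staff knowledge of carriage cannot change a culture result. It can affect which symptoms are elicited, which lesions are noticed and whether a lesion is swabbed. A reader might infer that unmasked staff make the outcome unreliable as a whole; the case definitions do not support that.

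**Much carrier time is not on weekly follow-up.** This also stands. Participants already positive at MV0 stay on monthly visits unless they become positive again after a negative swab, and weekly visits end after two negatives. The protocol summary confines weekly carrier swabbing to those who become positive in the first six months, although sections 3.2.2 and 5.3.6 state no limit. A reader might conclude that the whole objective 2 association is inflated by 1.1 to 2.6, or that only the 16 intensified households ever have equal surveillance. Neither follows. If the summary governs, later new carriers would not start weekly visits.

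**Dropping the weekly-visit detections is not neutral.** This is correct, and the working shows it. The restricted estimate can fall below the truth, so it should not replace the full one as the main result.

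**Conclusion.** The point holds in a limited form. During weekly carrier follow-up, the association between individual carriage and clinical infection is biased upward whenever self-report is incomplete. The direction follows from the protocol's own schedule, provided weekly-visit detections are counted. The size does not: about 1.1 to 2.6 under a true ratio of 1 rests on assumed 7–14 day episodes and 20–80% self-report, and the figure is smaller over all carrier time. The estimate restricted to monthly and participant-initiated detections runs from 1.00 down to about 0.68 under the same model for s of 0.2 or more, before any pre-empted self-reports. Both figures assume that being followed weekly does not itself change a person's readiness to phone.

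Two further inferences are not supported. The ratios of 2 to 3 in section 8 might be taken as a yardstick for this bias, but they concern risk factors for carriage, with carriage as the outcome; no power is stated for infection given carriage. Nor does the bias undercut the rationale for mass treatment in section 1.2, where the argument about carriage is onward spread to others, not the carrier's own risk of disease.

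**What to change.** 1. Record for each infection how it was first detected: monthly visit, participant-initiated contact, weekly carrier visit, or weekly intensified-household visit. Table 1 lets unscheduled-visit procedures take place at scheduled visits, so without this field the routes could be merged.
2. For objective 2, report two estimates side by side: all detected infections (biased upward), and only those first detected at monthly visits or by participant-initiated contact (biased downward). Draw the conclusion from the bracket, and tabulate weekly-carrier-visit detections separately.
3. Show the six-week block of the 16 intensified households as a descriptive equal-surveillance check only, because about 18 person-years will give few events.
4. Reconcile the protocol summary, which limits weekly carrier swabbing to those positive within the first six months, with sections 3.2.2 and 5.3.6, which state no limit. This determines how much person-time is affected.

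The cost is one data field, some protocol and SAP wording, a little more analysis and a less definite estimate. No visit, sample or aspect of care need change for items 1 to 3.

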5.3.7 Nested cross-sectional study of personal hygiene behaviour

At a one monthly visit, participants will be requested to undergo an additional survey on their personal hygiene behaviours for the last week including laundry, hand-washing, bathing and soap and disinfectant use. Attitudes towards wound-care and usual practices of participants in response to wounds will be captured.

At the same monthly visit, additional environmental swabs will be collected from the household including 4 commonly touched locations within the household and a sample of water from the main household greywater source. The swabs will be cultured as described in section 5.6.2.

These data, combined with individuals' carriage and infection data from the wider study will be used to assess the relationship between individual and household-level hygiene behaviours and GAS, GCS/GGS and *S. aureus* carriage, infection and reservoir presence within households in this setting.

5.4 Study visit and sampling schedule

Table 1. Visit data and sampling schedule for the various cohorts *only at MV0 and MV12

Visit timing	Visit window	Data and samples	Main cohort	Incidence cohort (16 households)	Duration cohort (new carriers)
-	Eligibility	X	-	-	
	Sociodemographics	X	-	-	

Month 0 enrolment visit (MV0)		Social mixing behaviour	X	-	-
		Household setup	X	-	-
		Medical history	X	-	-
		Physical examination	X	-	-
		Oropharyngeal swab	X	-	-
		Normal skin swab	X	-	-
		Blood serum*	X	-	-
		Dried blood spot	X	-	-
		Salivary sample	X	-	-
		Environmental swabs	X	-	-
		Settle plates	X	-	-
Weekly visits	+/- 7 days	Medical history	-	X	X
		Extended social-mixing behaviour	-	X	-
		Physical examination	-	X	X
		Oropharyngeal swab	-	X	(X) if previously positive
		Normal skin swab	-	X	(X) if previously positive
Monthly visits (MV1, MV2, MV3 etc. up to MV12)	+/- 14 days	Update sociodemographics	X	X	-
		Medical history	X	X	-
		Social-mixing behaviour	X	-	-
		Extended social-mixing behaviour	-	X	-
		Update household setup	X	X	-
		Physical examination	X	X	-
		Oropharyngeal swab	X	X	-
		Normal skin swab	X	X	-
		Blood serum*	X	X	-
		Dried blood spot	X	X	-
		Salivary sample	X	X	-
		Environmental swabs	X	X	-
		Settle plates	X	X	-
Unscheduled visits (may	-	Clinical history	X	X	X
		Physical examination	X	X	X

occur at scheduled visits if symptoms present)	Wound or throat swab	(X) if applicable	(X) if applicable	(X) if applicable
	Salivary sample	(X) if applicable	(X) if applicable	(X) if applicable
	Blood sample	(X) if applicable	(X) if applicable	(X) if applicable
Personal hygiene visit (done at another monthly visit	Personal and household hygiene questionnaire	X		
	Extended environmental swabbing	X		

5.5 Clinical and field evaluations

5.5.1 Socio-demographics and household set-up

At the enrolment and later visits where necessary, a series of questions will be asked of each individual participant in relation to their socio-demographic information including their date of birth, sex, tribal group, education and occupation. Any relevant medical information that is identifiable from ante-natal cards (ANC), or infant welfare cards (IWC) (especially for younger children) will be recorded such as birthweight, previous medical diagnoses and allergies.

For each household data will be collected relating to the household set-up including the number of buildings, number of rooms, accessibility for non-household members, sleeping arrangements, mosquito net use/coverage, household income, water access and proximity to community meeting points.

At subsequent monthly visits, individuals will be asked to briefly update some of their sociodemographic details such as occupation, school attendance and any other factors that may change throughout the year, and to complete any missing data. Similarly, alterations to household set-up will also be collected.

5.5.2 Social-mixing behaviour

For all participants at enrolment and monthly visits, and in more detail for the incidence cohort at each monthly visit, questions will be asked of individuals regarding their social-mixing behaviour. These questions will attempt to capture details about individuals' frequently visited places outside the household. They will be asked which places they visit, such as school, a workplace, shops, markets, places of worship, and how frequently they visit them. The location and proximity of these places will be mapped using GPS data by the field team. For the more detailed extended social-mixing behaviour collected in the intensified swabbing cohort, we will collect data on places visited in the form of a daily diary, listing with as much detail as possible the locations visited, people spent time with in close-proximity and events attended.

5.5.3 Medical and drug history

At enrolment, a focused past medical history will be taken from each individual including any regular medication taken, vaccination history, previous diagnoses and previous history of skin or throat infections specifically. Also at enrolment and at each subsequent visit for all cohorts, a brief history of recent medication (particularly antibiotics) and current clinical symptoms will be taken, including details of any recent healthcare setting attendance including traditional healers.

At unscheduled visits, a clinical history of the presenting complaint, medication usage and healthcare attendance will be taken to capture information related to any potential GAS infections, but also to inform immediate and subsequent medical management of other complaints.

5.5.4 Clinical examination and vital signs

At the enrolment visit, all participants will undergo a physical examination including vital signs to provide a baseline. Vital signs collected will include axillary temperature, pulse rate and respiratory rate. Adults (over 18 years) will also have blood pressure recorded.

Participants will then undergo a physical examination which will include an examination of the pharynx and associated lymph nodes, and a full body examination of the participant's skin, to identify any pyoderma lesions, and other relevant skin conditions. Care will be taken to perform the full body examination with appropriate privacy and verbal consent obtained at the time. Portable screens will be used to maintain privacy when necessary. Participants' genitals will only be examined if they specifically report (or the parent reports, in the case of children) the presence of a lesion and verbally consent for the study nurse examine them.

At later scheduled visits, monthly visits for the main cohort, and weekly visits for the more intensive cohorts, participants will undergo the physical examination including throat and skin, but will not have vitals and anthropometry recorded unless they are reporting symptoms suggestive of a GAS infection. If they are symptomatic, a clinical history will be taken and fuller clinical examination of the presenting complaint will be done, in addition to recording vital signs.

At unscheduled visits participants will also have their vitals recorded in the same way, and a clinical history and focused clinical examination will be done.

